c.5. Preliminary Studies. This is a feasibility study so no preliminary data for this protocol have been collected. [name] has recently successfully developed and tested a standardized acupuncture protocol for the treatment of women with vulvodynia⁶⁵. [name], has extensive expertise in symptoms, gender, and measurement and has received substantial extramural (F31, T32, R15, R01) and intramural funding for her cardiovascular research. She has developed a validated symptom checklist for patients with acute coronary syndrome and has been funded on several studies to examine the acute and chronic symptoms of IHD⁶⁶⁻⁶⁸.

c.6. Methods

c.6.1. Sample & Setting. Sixty-nine women and men, with a confirmed diagnosis of chest pain or stable angina will be included. We will recruit women from the Chicago metropolitan area including the UIC campus community. Inclusion criteria are: provision of a verified diagnosis from a care provider, individual, ≥ 21 years of age (since IHD presenting as angina has not been reported in children), chest pain or intermittent angina symptoms (pain, pressure, or discomfort in the chest or other areas of the upper body), and medical confirmation of a diagnosis of stable angina. Exclusion criteria include pregnancy, , COPD causing pain or associated symptoms, autoimmune dysfunction, use of steroid medications, and concomitant, biofeedback, or additional acupuncture. Participants will be instructed to continue medications to treat their chest pain or angina, as well as other health conditions, as prescribed. Etiology of chest pain or angina (i.e. occlusive coronary artery disease, microvascular disease, or vasospastic ischemia) is not an inclusion criteria. Menopausal status will be adjusted for in statistical analyses.

The study will be conducted at the University of Illinois, College of Nursing (UIC CON) in clinical research exam rooms on the fourth floor. One Illinois licensed acupuncturist, [name], whose qualifications are described in the budget justification will be administering all 10 acupuncture treatments to 35 experimental participants (and up to 34 control group participants upon study completion) there. The exam rooms will also be utilized to obtain informed consent and for research data collection. The UIC CON is accessible by public transportation and has parking available nearby.

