c.6.2. Power Analysis. This feasibility pilot study is not powered to detect significant effects for improvement in symptom outcome measures. However, In order to achieve 80% power to detect a large effect size using Cohen's classification ($EF=.80$), 52 patients randomized and completing the final symptoms assessments will be needed. Based on our sample of 26 participants, we will be able to detect a Cohen's d effect size of 1.10 as statistically significant. While a large effect size is not anticipated in this pilot feasibility study, an expanded trial will be adequately powered to explore the threshold for a clinically meaningful effect.

c.6.3. Retention Strategies. We anticipate an attrition rate of no more than 10%, which means we expect a 90% retention rate for the subjects. These numbers are based on accruals and withdrawals in [name] previous 10 session acupuncture trial for which there were 36 accruals and no withdrawals. The following retention strategies will be employed: Participants will be engaged as active partners in the research by addressing possible benefits of acupuncture (experimental group) and non-pain related health education (control group) as well as the importance of their contribution to science. Data collection will be scheduled at convenient times for participants, including weekend and evening appointments. Multiple contact information (e-mail, cell phone, and home phone) will be collected to improve adherence to appointments. We also will offer \$10 per visit to cover the cost of travel.

c.6.4. Procedures. The research assistant will screen and consent eligible individuals. The potential participants will be informed that they will either be randomized to the acupuncture group (10-acupuncture session protocol, two treatments per week for five weeks) or the attention control group. Data will be collected on tablet computers before and after each session. Control group members will be offered the acupuncture protocol at study completion.

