c.7.1.g. **Biomarkers of Inflammation**. Proinflammatory cytokines IL-1 β , IL-2, IL-8, and IL-18; CRP^{76,77}; and TNF α , the anti-inflammatory cytokines IL-4, and IL-10,⁷⁶ and the dual pro/anti-inflammatory IL-6⁷⁸ will be measured to determine if there is a significant change baseline to post study (5 week). Venous blood (4.5 mls) will be collected in a blue-top tube containing 3.2% sodium citrate. Samples will be processed in our clinical lab in the college. Samples will be centrifuged at room temperature for 15 minutes; plasma will be removed into 2 cryovials in 1 ml aliquots and stored in a -80°C freezer immediately. A label with study ID number, date, and time of blood draw will be placed on the cryovials prior to freezing. Samples will be batch analyzed using high-sensitivity multiplex technologies.⁷⁹ See **Table 1** for all variables, measures, and data collection time points.

c.8. Potential Problems, Alternate Plans, and Limitations based on the Sample Proposed. Rigorous research into complementary and alternative therapies has been hindered by the inability to conduct placebo-controlled trials⁸⁰. Our attention control design is a strong alternative to an intervention that cannot be blinded to participant or interventionist without potential confounding treatment effects. Recruitment is always a potential problem with clinical research and we will enlist the help of the American Heart Association Chicago Affiliate and *WomenHeart* of Cook County to identify potential participants. Attrition is also a possible problem but [name] has experienced very little attrition in prior acupuncture studies. We will continue to enroll to retain 24 participants and we will address attrition with an intention to treat analysis. Design limitations were addressed in section c.3.

Table 1. Data Collection Variables, Measures, and Time Points (Both Groups)

Variable	Measure/Analyses	Data Collection Points (Baseline) (10 tx sessions) (5 wks.)		
Aim 1				
Recruitment	Number enrolled/number invited to participate	X		X
Retention	Number retained at study completion/number recruited	X		X
Completion	Number of time points completed/12 (total)	X		X
Acceptability	Protocol Acceptability Scale for Treating Angina with Acupuncture			X
Aim 2				
Effect Size	Intra-individual effect : mean pre-scores – mean post-scores/pooled s.d. Group effect : mean differences in scores between acupuncture and attention control group.	X		X

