Demographic Data	Demographic Data tionsForm	X		
Exploratory Aim				
Biomarkers	Interleukin 1 β , 2, 6, 8, 10 & 18; CRP, TNF- α	X		X
Outcome Measures				
Pain & Symptoms	McGill Pain Questionnaire; Seattle Angina Questionnaire-7; AHA Angina Log	X	X	X
Acupuncture Sensations	MASS		X	

Note: TX is treatment. s.d. is standard deviation. AHA is American Heart Association

c.9. Statistical Analysis. [name] will supervise data management and data analysis procedures. We will address missing data by intention to treat analyses (ITT), using the full information maximum likelihood (FIML) approach, which has been shown to produce unbiased parameter estimates and standard errors when data are missing at random⁸¹⁷⁷⁷⁶⁷⁶⁷⁶⁷⁶⁷⁶⁸³. All data will be exported from RedCap and imported into SAS version 9.4 for cleaning and analysis. All variables will be screened and descriptive statistics (frequencies, means,

standard deviations) will be used to describe the sample participants. Non-normal distributions may be optimally transformed using the Box-Cox method and/or analyzed using a comparable non-parametric test.

c.9.1. Aim 1: To determine the feasibility of study processes (recruitment, retention, completion, acceptability) to inform the design and execution of a future R21 study.

Hypothesis: Acupuncture therapy will be feasible (80% recruitment, retention, completion) and acceptable to individuals with chest pain or stable angina.

For the feasibility assessments descriptive statistics will be used for describing the subject characteristics and recruitment, retention & completion. We will explore patient characteristics that predict attrition and/or poor adherence to the treatment schedule. Data collected at every session will be explored to assess change in pain ratings following a session and if this pattern is consistent over the course of treatment. We are interested in knowing if pain and other symptom relief continues to improve linearly over the 5 weeks and 10 treatments or if a plateau is reached suggesting the need for fewer treatments.

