c.9.2. Aim 2: To estimate effect sizes for pre and post intervention scores and between the acupuncture and attention control groups for pain/symptoms, functional status and QoL. We will estimate standardized mean difference effect sizes (Hedges' g) comparing the treatment and control conditions adjusting for baseline differences and the upward bias due to our small sample size. We will also compute a standardized pre-post difference for the treatment group. Effect sizes will be calculated for pain, angina symptoms reported via survey and diary, functional status, and quality of life.

c.10. Timeline. We will prepare study materials and submit an IRB application upon notice of award. Three months is allotted for IRB approval process. The study is anticipated to begin on June 1, 2016 and be completed on August 31, 2017. See Table 2 for study timeline.

Table 2. Study Timeline

Study Phase	(Jun-Aug 16)	(Sept-Nov 16)	(Dec-Feb 17)	(Mar-May 17)	(Jun-Aug 17)
Submit IRB appl.	→ → →				
Recruit/Train RA		→			
Data Collection		→ → →	→ → →	→ → →	
Data Coding/Entry			→ → →	→ → →	
Data Analysis				→ →	
R21 Preparation				→ →	→
Manuscript Prep					→ →

References

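### c.9 claims unbiased standard errors from FIML, but that is a large-sample property: at the plan's sample sizes they are about 6% (n = 24-26) to 2% (n = 69) too small

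*Combined protocol and SAP*

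**What the plan says.** Section c.9 commits to intention-to-treat analyses using a "full information maximum likelihood (FIML) approach, which has been shown to produce unbiased parameter estimates and standard errors" under missing at random. SAS 9.4 is the software. The text names no procedure, no choice between ML and REML, no reference distribution and no degrees-of-freedom method. The only small-sample correction in the document is in c.9.2, where Hedges' g is to be computed "adjusting for baseline differences and the upward bias due to our small sample size".

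Several sample sizes appear:
- c.6.1: "Sixty-nine women and men, with a confirmed diagnosis of chest pain or stable angina will be included", split 35 and 34.
- c.6.2: 52 completers for 80% power at an effect size of 0.80, and then a detectable effect of 1.10 "Based on our sample of 26 participants".
- c.8: enrolment continues until 24 are retained.

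Section c.6.2 also says that the pilot is not powered for symptom outcomes. The explicit reference to a significant result is in c.7.1.g, where the biomarkers are measured "to determine if there is a significant change baseline to post study (5 week" weeks); Table 1 places them under an exploratory aim.

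**The concern.** The plan recognises small-sample bias in its effect size, yet claims that the standard errors of its main estimation method have none. Under missing at random, FIML standard errors are correct as n grows. In small samples the ML variance is too low, because it makes no allowance for the mean parameters that were estimated. If a normal reference is used in place of t, intervals narrow further. Both errors run in the optimistic direction.

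At stake are the quantities that need a standard error: the biomarker change, the question in c.9.1 of whether relief continues linearly or reaches a plateau, the exploratory predictors of attrition and adherence, and any interval placed around g when the pilot is used to plan the next study.

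**Working it through.** **The plan's own figures.** The document gives no figure for a standard error or for coverage, so there is none to reproduce on this exact point. The sample-size figures that set the range do reproduce at two-sided alpha 0.05 (assumed; the plan states no alpha). At d = 0.80 and 80% power, the exact two-sample t calculation gives 25.5 per arm, so 26 per arm and 52 in total. With 13 per arm, the normal approximation gives a detectable d of 1.099.

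**Inputs.** n = 24 (c.8), 26 and 52 (c.6.2), 69 (c.6.1). Assumed: normal outcomes, complete data, and k = 3 mean parameters (intercept, arm, baseline).

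**Formulas.**
- SE ratio: r = sqrt((n - k)/n), the ML standard error over the one based on residual degrees of freedom.
- Coverage with a normal reference: P(|t| < 1.96 r), with t on n - 3 df.
- Coverage with a t reference: P(|t| < c r), where c is the 97.5% point of t on n - 3 df.

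| n | r | 1.96 r | Coverage, normal | c | c r | Coverage, t |
|---|---|---|---|---|---|---|
| 24 | sqrt(21/24) = 0.935 | 1.833 | 91.9% | 2.080 | 1.945 | 93.5% |
| 26 | sqrt(23/26) = 0.941 | 1.843 | 92.2% | 2.069 | 1.946 | 93.6% |
| 52 | sqrt(49/52) = 0.971 | 1.903 | 93.7% | 2.010 | 1.951 | 94.3% |
| 69 | sqrt(66/69) = 0.978 | 1.917 | 94.0% | 1.997 | 1.953 | 94.5% |

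With the normal reference, type I error is 7.8% at n = 26 and 6.0% at n = 69, against a nominal 5%.

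**Within-arm change.** Section c.9.2 also plans a pre-post effect in the treatment group. With one mean parameter, r = sqrt((n - 1)/n). For 13 in the arm, r = 0.961 and normal-reference coverage is 91.6%. For 35, r = 0.986 and coverage is 93.8%.

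**With missing data.** A simulation of a baseline/post FIML model used 20,000 replicates, an assumed correlation of 0.5, a true difference of 0.8 SD, and about 10% missing-at-random dropout (the ceiling in c.6.3):

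| n | Mean ML SE / true SE | Coverage, normal | Same ratio, residual-df variance |
|---|---|---|---|
| 26 | 0.92 | 91.5% | 0.99 |
| 52 | 0.96 | 93.4% | 0.99 |
| 69 | 0.97 | 93.8% | 1.00 |

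The residual-df variance removes nearly all of the shortfall. In the same runs, g formed from the adjusted mean difference, the pooled observed SD and the Hedges factor averaged 1.00 times the true value, so the mean differences show no bias. The simulation has one post-baseline measure; it does not reproduce the unequal schedules of the two arms.

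**The case against.** The strongest reply is that little in this pilot rests on standard errors. Aim 1 is descriptive, Aim 2 names neither a test nor an interval, and c.6.2 disclaims power for symptom effects. The biomarker aim is exploratory with no named test, and c.9 allows a transformation or a non-parametric alternative. All of this stands, and it limits the consequence. It does not make the stated property true.

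A second reply is that 92% coverage combines the ML standard error with a normal reference that the plan never names. This is fair. With a t reference, coverage is 93.5% to 93.6% at 24 to 26, so part of the shortfall depends on a choice the plan leaves open. Third, at 69 the shortfall is about 2%, which is small for a feasibility study. That also stands. The larger figures apply only if 24 to 26 is the real sample size, and the conflict between the stated sizes is a separate matter.

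A reader might go further and infer that g will be scaled by a FIML or model-residual SD, and so regain the bias that c.9.2 promises to remove. The documents do not support this. Nothing in them scales g that way. Hedges' g ordinarily implies a pooled SD, and Table 1 names one for the intra-individual effect ("mean post-scores/pooled s.d."). For the group effect, Table 1 gives only "mean differences in scores between acupuncture and attention control group", with no denominator. That is a missing detail, not a planned error.

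**Conclusion.** The point holds in a limited form. The unqualified claim of unbiased standard errors in c.9 is not exact at any sample size in the plan. ML standard errors for a baseline-adjusted contrast are about 6% too small at 24 to 26 and about 2% too small at 69. Nominal 95% intervals cover about 92% and 94% with a normal reference, or about 93.5% and 94.5% with t.

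These sizes assume normal outcomes and three mean parameters. They do not carry over directly to a model of attrition as a yes/no outcome, or to a repeated-measures model over all sessions. The point concerns variances and what is built on them, and gives no reason to think that the estimated mean differences or g are biased. The change is worth making because a stated property is wrong and the remedy is cheap; no main conclusion of the pilot hangs on it.

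**What to change.** In c.9:
- Fit the models for continuous outcomes by REML in SAS 9.4, with Kenward-Roger standard errors and degrees of freedom. Keep the missing-at-random assumption and every randomised participant with a score, for example by entering baseline among the responses.
- Name in advance a parsimonious covariance structure that accommodates the two measurement schedules: after 10 sessions in the acupuncture arm (c.6.5) and at 5 timepoints in the control arm (c.6.8).
- Delete the claim of unbiased standard errors, or qualify it as asymptotic.

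As a clarification only, state in c.9.2 that the group-effect g is the baseline-adjusted mean difference divided by the pooled observed SD (denominator n1 + n2 - 2), and then multiplied by the Hedges factor.

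The cost is a few sentences of analysis text and one real decision, the covariance structure. Software and data are unchanged. Intervals become slightly wider.
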